### **7.2.3 Withdrawal of Patients**

Patients/caregivers will be informed that they have the right to withdraw from the study at any time, without prejudice to their medical care, and that they are not obliged to state their reasons.

Any withdrawal, and reasons for withdrawal, must be fully documented in the electronic case report form (eCRF) and source documents and the patient followed by the investigator/investigative staff. Even after the study is completed at the Follow-up Visit, the investigator/investigative staff will, regardless of reason for withdrawal, record any patient data they receive concerning SAEs, and all drug-related non-serious AEs, and subsequently report these according to Section 10.1. Withdrawn patients will not be replaced.

Patients will be withdrawn in the following circumstances:

- A patient's/caregiver's desire for withdrawal for any reason
- Lost to follow-up (every effort must be made to contact the patient/caregiver; a certified letter must be sent)
- An AE that, in the opinion of the investigator, necessitates withdrawal
- A worsening of the symptoms related to diarrhea occurs
- Death
- Patient/caregiver estimation of intolerable symptoms
- A patient's/caregiver's substantial noncompliance (eDiary and study drug compliance) or protocol violation
- An investigator's opinion that continuing the patient in the study is not appropriate. The investigator may withdraw a patient at any time, if it is considered to be in the patient's best interest

A patient who prematurely withdraws due to intolerable symptoms, and has completed at least 12 weeks treatment in the double-blind study, will be offered the opportunity to enter open-label Study A4250-008. A patient who withdraws from treatment prematurely and does not enter Study A4250-008 will have EOT (Visit 9) assessments at the time of withdrawal and a follow-up assessment (Visit 10) 28 days following the last dose of study drug, and the patient will be recorded as withdrawn.

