**If any ONE of the following criteria are met:**

1. Transaminases (ALT or AST  $\geq 3 \times$  baseline or 800 U/L, whichever comes first) AND bilirubin (total bilirubin  $> 2 \times$  ULN) elevations

2. Transaminase elevations alone (ALT or AST  $>10 \times$  ULN or  $5 \times$  baseline or absolute threshold of 800 U/L, whichever comes first) in presence of normal LDH and CPK
3. Total bilirubin increased, unrelated to hemolysis (elevated reticulocyte count) or established genetic diseases, such as Gilbert's syndrome
  - a. Doubling if total bilirubin was  $<3$  mg/dL (equivalent to  $51.3 \mu\text{mol/L}$ ) at baseline
  - b. OR Increase by  $>3$  mg/dL (equivalent to  $51.3 \mu\text{mol/L}$ ) if total bilirubin was  $\geq 3$  mg/dL (equivalent to  $51.3 \mu\text{mol/L}$ ) at baseline
4. INR increase refractory to vitamin K administration
  - a. INR  $>1.5$  if INR was normal at baseline
  - b. OR Increase by  $>0.4$  if INR was abnormal at baseline
5. Any increase in total bilirubin and transaminases if accompanied by EITHER a symptom of clinical hepatitis (e.g., vomiting, nausea, right upper quadrant pain) OR immunological reaction (rash or  $>5\%$  eosinophilia)

Then:

- a) Interrupt study medication
- b) Initiate drug-induced liver injury work-up for alternative etiologies
- c) Repeat liver profile (AST, ALT, total bilirubin, direct bilirubin) and PT or INR within 48 to 72 hours
- d) Monitor the patient using close observation found in Section 10.2.2.2
- e) If a patient lives in a remote area, they may be tested locally and the results communicated to the investigator site promptly

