### **10.2.2.4 Diarrhea**

Study drug should be discontinued if a patient develops diarrhea with at least 1 of the following concomitant signs or symptoms: grossly bloody stools, vomiting, dehydration requiring treatment with oral or intravenous rehydration and/or electrolyte imbalances, fever ( $\geq 38$  C) and/or the diarrhea persists for 7 or more days.

If there is gross blood in stool, INR and platelets should be measured.

Study drug will be reintroduced (re-challenge) when the symptoms have resolved. If the diarrhea re-occurs within 1 week after the re-challenge with no alternate etiology, the patient will be permanently discontinued and monitored as outlined in Section 10.2.2.5.

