#### **11.2.2.2 Missing Data**

In the primary analysis of the pruritus endpoint, all intermittently missing assessments will be classified as negative pruritus assessments. Similarly, all planned assessments after the intercurrent events (premature treatment discontinuation, death or initiation of rescue treatments such as biliary diversion surgery or liver transplantation) will be counted as negative pruritus assessments. However, as described above, all 336 assessments planned over the 24-week treatment period will be included in the denominator of the endpoint definition.

In the primary analysis of fasting bile acid responder endpoint, dropouts and patients with a missing average at the end of the treatment will be treated as non-responders. Patients in need of surgical rescue, i.e. biliary diversion and listing for liver transplant will be classified as non-responders. Continued collection of efficacy data for patients who discontinue treatment will be made as far as possible.

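### Section 7.2.3 makes any worsening of diarrhea symptoms a mandatory withdrawal, without a threshold or a link to the hold-and-re-challenge rule in Section 10.2.2.4

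*Protocol*

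**What the plan says.** Two sections of the protocol govern a child with diarrhea.

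- **Section 7.2.3 (Withdrawal of Patients)** opens its list in mandatory terms: patients will be withdrawn in the circumstances named. One of these is "A worsening of the symptoms related to diarrhea occurs". The bullet gives no grade, duration, accompanying sign, causality or investigator judgement. The bullet directly above it, on adverse events, does depend on the investigator's opinion. The section adds: "Withdrawn patients will not be replaced".
- **Section 10.2.2.4 (Diarrhea)** sets a graded rule. "Study drug should be discontinued if a patient develops diarrhea with at least 1 of the following concomitant signs or symptoms". The list is visible blood in stool, vomiting, dehydration needing rehydration and/or electrolyte disturbance, or fever of at least 38 °C. Diarrhea lasting 7 days or more also qualifies. Then: "Study drug will be reintroduced (re-challenge) when the symptoms have resolved". The final stop is narrow: "If the diarrhea re-occurs within 1 week after the re-challenge with no alternate etiology, the patient will be permanently discontinued".

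Neither section cites the other, and no text in the file says which prevails. The earlier protocol versions in the file carry the same bullet and the same re-challenge rule.

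**Section 11.2.2.2 (Missing Data)** fixes what a withdrawal means for the two primary endpoints. For serum bile acids, "dropouts and patients with a missing average at the end of the treatment will be treated as non-responders". For pruritus, "all planned assessments after the intercurrent events (premature treatment discontinuation, death or initiation of rescue treatments" such as biliary diversion or transplantation are counted as negative, within a fixed denominator of 336.

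**The concern.** A site that follows 7.2.3 as written withdraws a child at the first worsening. A site that follows 10.2.2.4 holds drug, waits for resolution and re-challenges, or keeps dosing if the threshold is not met. The same child can therefore be handled in two ways, and the choice carries into both primary endpoints.

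The risk is unlikely to be equal across arms. Section 5.3.1 of the 10 May 2018 version in the file says that loose stools or diarrhea could be expected from the drug's mechanism. Avoidable withdrawals would then fall mainly on the two active arms. Each one removes a child who might have responded, and the child is not replaced.

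**Working it through.** **Step 1. Apply both rules to the same child on study drug.**

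| Case | Section 7.2.3, read literally | Section 10.2.2.4 |
|---|---|---|
| Diarrhea worsens and vomiting appears | Withdraw | Stop drug, re-challenge once resolved |
| Diarrhea worsens, no listed sign, under 7 days | Withdraw | No stop |
| Held, re-challenged, recurs within 1 week, no alternate etiology | Withdraw, if the recurrence counts as worsening | Permanent discontinuation |
| Diarrhea worsens or persists while drug is held | Withdraw if it worsens; persistence is not named | No disposition given |

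The rules diverge in the first two rows. The third is compatible. The fourth is a gap in 10.2.2.4 that the 7.2.3 bullet partly covers. Reading 7.2.3 as leaving the study and 10.2.2.4 as stopping the drug does not remove the divergence, because a withdrawn child cannot be re-challenged.

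**Step 2. Bile acid power, as an upper-bound illustration.** No diarrhea withdrawal rate is documented, so the losses are assumed.

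- Inputs from Section 11.1: 60% response on A4250, 10% on placebo, 20 per arm, one-sided 0.025, closed procedure (pooled doses first, then each dose).
- Method: exact enumeration of three binomial arms in a single stratum, one-sided Mantel-Haenszel test with z ≥ 1.96. Placebo is Bin(n, 0.10). With k children lost per active arm, active responders are Bin(n − k, 0.60) and the denominator stays n, since dropouts count as non-responders.

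| n per arm | Lost per active arm (k) | A given arm | At least one arm | Both arms |
|---|---|---|---|---|
| 20 | 0 | 94.9% | 98.3% | 91.5% |
| 20 | 1 | 92.7% | 97.2% | 88.1% |
| 20 | 2 | 89.6% | 95.5% | 83.8% |

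The no-loss row is close to the protocol's own simulated values of approximately 94%, 99% and 91%. At 23 per arm (3 × 23 = 69, within the planned 60 to 70), one loss per active arm moves power for a given arm from 96.9% to 95.6%.

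These are upper bounds for the stated losses. They credit every lost child with the full 60% chance of response had 10.2.2.4 been followed, although some re-challenges would fail.

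**Step 3. Pruritus.** Two entries a day over 24 weeks give 14 × 24 = 336. A child withdrawn at week t has 14 × (24 − t) entries set negative. If all of those would have been positive, one child in an arm of 20 lowers the arm mean by (1/20) × (24 − t)/24.

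| Assumed week t | Entries set negative | Largest fall in arm mean |
|---|---|---|
| 4 | 280 | 4.2 points |
| 12 | 168 | 2.5 points |
| 20 | 56 | 0.8 points |

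**The case against.** The strongest reply is that the rules are complementary. Section 10.2.2.4 allows re-challenge only on resolution, and worsening presupposes diarrhea already present. On this view, diarrhea that resolves leads to re-challenge and diarrhea that worsens leads to withdrawal, so the 7.2.3 bullet supplies the exit for a child who deteriorates off drug. A site would also naturally manage diarrhea from the section with that heading. This reading is possible, and it rules out calling the two sections irreconcilable. It does not settle the matter, because the bullet is not limited to the hold or to failed re-challenge and reaches a child still on drug.

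Three further points stand.

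- A bullet that referred only to the present permanent-discontinuation rule would remove the one mandatory exit for diarrhea that worsens during the hold. The fix has to cover that case.
- A held child is not assured of a better score. A failed re-challenge ends as premature treatment discontinuation, with the same scoring.
- The 5.3.1 text cited comes from an earlier version in the file. It reports only one mild, transient case of diarrhea in the pediatric phase 2 study, which did not recur on multiple dosing. That suggests the trigger may seldom be met.

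A reader might also infer that sites will misread 10.2.2.4 because it calls the temporary stop a discontinuation, while the liver rules say "Interrupt study medication". The text does not support that: reintroduction follows directly, so the first stop is plainly temporary. This is a matter of style.

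**Conclusion.** The point holds as a minor one. A mandatory withdrawal trigger without threshold or cross-reference, taken literally, withdraws children whom the specific diarrhea rule would keep in the trial. Its author may have meant something narrower, but the text does not say so.

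A reader might infer that the primary results or the trial's power are materially compromised. The documents do not support that. Avoidable withdrawals lower the active arms' scores, so the effect runs against the drug and does not inflate type I error. Its size is undocumented, and the power and pruritus figures are ceilings on assumed losses, not forecasts. That losses would fall mainly on the active arms is an inference from the mechanism.

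One limit remains: only part 2 of 3 of the file is available, so wording in the parts not shown could not be checked.

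**What to change.** - In Section 7.2.3, replace the diarrhea bullet with: *Diarrhea requiring permanent discontinuation per Section 10.2.2.4*.
- In Section 10.2.2.4, extend permanent discontinuation to diarrhea that worsens or fails to resolve while study drug is held, alongside recurrence within 1 week of re-challenge with no alternate etiology.
- Keep the investigator-judgement adverse event bullet and the best-interest bullet in 7.2.3.
- Optionally, use *interrupted* for the temporary hold in 10.2.2.4, to match the liver rules.

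The cost is one bullet and one added clause at the next amendment, with no new visits, data or analyses. The downside is that a blanket mandatory withdrawal is narrowed: milder worsening is left to 10.2.2.4 and the investigator's judgement.

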#### **7.2.4 Study Termination by Sponsor**

This study may be terminated at any time by Albireo if serious side effects should occur, if the investigator does not adhere to the protocol; or if, in the sponsor's judgment, there are no further benefits to be achieved from the study. In this event, Albireo/designee will inform the study investigators, institutions, and all regulatory authorities.

Albireo may temporarily or permanently discontinue the study at an investigative site at any time for safety, ethical, compliance, or other reasons. If this is necessary, Albireo will endeavor to provide advance notification to the site. If a site or the study is suspended or discontinued, the investigator/investigative staff will be responsible for promptly informing the Independent Ethics Committee (IEC). If required by local regulations, Albireo/designee will be responsible for informing the IEC and the regulatory authority of study or site discontinuation. In such an event, all study data and unused study drug must be returned to Albireo.

## **8 TREATMENT OF PATIENTS**

### **8.1 Identity of Study Drug**

A4250 and placebo will be supplied as capsules for oral administration. White opaque capsules filled with pellets containing A4250 or placebo will be provided. Two different capsule sizes will be available, as follows:

- Capsule size 0 that can be opened
- Capsule size 3 that should be swallowed intact. These size 3 capsules may be opened only under exceptional circumstances, e.g., patient cannot swallow capsule intact

The content of the A4250 and placebo capsules will be identical in appearance. Capsule filling weight will also be identical for high dose, low dose, and placebo. Bottles with 34 capsules will be given to the patient at each visit. A patient who requires 2 or more capsules per day will be given multiple bottles. Refer to the investigational product manual.

### **8.2 Administration of Study Drug**

Patients will be dosed with A4250 at a dose of 40 µg/kg/day, 120 µg/kg/day, or placebo for 24 weeks. Study drug will be dispensed to the patient at Visits 3, 4, 5, 6, 7, and 8, together with instructions on how to store and take the drug. Study drug administration data, including whether each patient took each dose or partial doses of study drug, whether there were any delayed or missed doses, and whether the capsule was opened or swallowed whole will be documented through the eDiary and transferred to the study database.

A4250 should be taken in the morning, together with food. On clinic visits days when laboratory assessments are conducted, study drug should be taken after the visit and after laboratory samples are taken. Patients should not crush or chew the capsule(s). When swallowing the capsule intact, the patient should administer the dose with a glass of water.

For a patient unable to swallow capsule intact, the capsule can be opened and the contents sprinkled and mixed in a small amount of soft room-temperature yogurt, apple sauce, or fruit purée. A list of food options can be found in the Pharmacy manual. The amount of food should be less than what the patient/infant is expected to eat and should be followed by water.

1. Hold the capsule over the prepared food, gently twist open and allow the content to fall into food
2. Mix the entire capsule content with 1 or 2 tablespoons (15 to 30 mL) of soft food (apple sauce, fruit purée, or yogurt)
3. Administer the mixture immediately after mixing.

The number of capsules provided to the patient will be based on body weight at Visit 3. At Visit 6, if a patient's weight has shifted to another weight category (identified in [Table 2](#)), the number of capsules per day may be adjusted.

**Table 2 Dosing and Capsule Strength**

Body Weight (kg)	Capsule Size	Number of Capsules per Day	Capsule Strength, Low Dose (µg)	Total Dose (µg)	Capsule Strength, High Dose (µg)	Total Dose (µg)	Capsule Size, Placebo (µg)
5.0 to <7.5	0	1	200	200	600	600	0
7.5 to <12.5	0	2	200	400	600	1200	0
12.5 to <17.5	0	3	200	600	600	1800	0
17.5 to <19.5	0	4	200	800	600	2400	0
19.5 to <25.5	3	2	400	800	1200	2400	3
25.5 to <35.5	3	3	400	1200	1200	3600	3
35.5 to <45.5	3	4	400	1600	1200	4800	3
45.5 to 55.5	3	5	400	2000	1200	6000	3
>55.5	3	6	400	2400	1200	7200	3

### 8.3 Study Treatment Packaging and Labeling

#### 8.3.1 Packaging and Labeling

The capsules will be packed in high-density polyethylene containers, with child-proof polypropylene caps. Study drug capsules containing A4250 in the strength specified in Table 2 above will be manufactured.

Packaging and labeling will be prepared to comply with applicable regulatory requirements.

#### 8.3.2 Storage

Treatment packs containing A4250 capsules should be stored and dispensed in accordance with regulations in their original containers. The storage facility at the investigative site should be locked and the storage temperature should be between 15°C and 25°C.

Patients/caregivers should be informed of appropriate storage conditions (i.e., room temperature, between 15°C and 25°C).

Any deviations from the recommended storage conditions should be immediately reported to Albireo and the study drug should not be used until authorization has been given by Albireo.

#### 8.3.3 Blinding and Randomization of Study Drug

A double-blind design is employed so that both the investigators and the patients will be unaware of the treatment assignment during the study.

After written informed consent is obtained from an eligible patient, an 8-digit patient identification number will be assigned. The first 2 digits will denote the country, followed by a 3-digit site number and a 3-digit patient sequence number. This number will be created and

allocated by the Interactive Web Response System (IWRS), when the patient first enters the system at Screening. The randomization codes will be computer-generated by [REDACTED] Biostatistics, and kept by a statistician independent from the project team. The randomization will be done in blocks and stratified according to PFIC class (Type 1 and 2) and age class (6 months to 5 years, 6 to 12 years, and 13 to  $\leq 18$  years) to ensure approximate balance between dose schemes (1:1:1). A separate randomization list will be prepared for the maximum 5 patients from Study A4250-003 regardless of stratification. Randomization codes will be assigned sequentially as patients become eligible for randomization.

Patients who are eligible for randomization will be assigned a unique 4-digit randomization number by IWRS. This randomization number identifies which treatment will be allocated to the patient. Patients who withdraw from the study after randomization visit are not to be replaced and their randomization number will not be reused.

To ensure blinding, the study drug and the matching placebo have the same shape and size. Patients will receive capsule(s) of A4250 according to their dose group or capsule(s) of matching placebo once a day during the double-blind Treatment Period. Labels on the study drug containers will not identify the treatment that a patient is randomized to. Traceability of the treatment is ensured by the study drug number.

The 5-digit study drug number will identify study drug packs and will be detailed on the study drug label. Dispensing of study drug will be coordinated by IWRS.

The system will assign a study drug number corresponding to the randomization arm. The randomization number will be used in the background only to ensure no unblinding and will not be displayed to end-users in the IWRS.

#### **8.4 Procedure for Breaking the Randomization Code**

Should a situation arise where unblinding is urgently required, i.e., only where knowledge of the study drug is required to adequately manage a life-threatening situation, the investigator at that study site may perform immediate unblinding through IWRS. The responsibility to break the treatment code in emergency situations resides solely with the investigator. The investigator should make every effort to discuss the rationale (status and outcome) for emergency unblinding with the sponsor Medical Monitor or the [REDACTED] Medical Monitor as soon as possible to review the individual patient details.

The study site investigator and appropriate [REDACTED] project team members will be authorized to access the emergency unblinding functionality within the IWRS. Emergency unblinding takes place in the IWRS via a dedicated emergency unblinding module. The system will require the user to enter their emergency unblinding, which is typically provided at the same time login credentials are distributed. The exact description of the treatment assigned to the individual patient then will be accessible to the user. Once the randomization code is broken for a patient, he/she must be withdrawn from the study and all assessments and procedures at EOT should be performed. As a follow-up, Visit 10 will be performed according to the time

schedule. Once a randomization code has been broken, the investigator must inform the [REDACTED] and sponsor Medical Monitor in writing within 24 hours. In case of technical issues accessing the system online, please see the IWRS site user manual for country-specific contact telephone numbers for the [REDACTED] HelpDesk 24/7 system support.

### **8.5 Patient Compliance**

The study nurse will monitor eDiary compliance by routine review of the CRF health website. If both diary entries on a day are missing, the study nurse will call the patient/caregiver to remind them to complete all scheduled entries. Any noncompliance will be documented and explained in the source documents.

Study drug compliance will also be checked through diary responses. Additionally, patients will return all unused study drug at Visits 4, 5, 6, 7, 8, and 9. The study site staff will count all returned drug, assess compliance, and record details in the eCRF.

Treatment Compliance =  $100 \times ((\text{Number of study drug dispensed} - \text{number of study drug returned}) / \text{number of study drug that should be taken})$ .

Treatment compliance between 80% and 120% will be acceptable.

